Primary Outcome: Age and sex will be entered as covariates in all appropriate analyses if between group differences exist. To test study hypotheses, a 2 (group) X 2 (rest vs. manipulation) X 3 (naloxone vs. saline) repeated measures (RM) ANOVA will be employed. Post-hoc paired samples t-tests (in each group) will be conducted to test the hypotheses that non-mindfulness meditation but not mindfulness induced analgesia will be reversed by administration of naloxone but not saline.

Exploratory analyses may be conducted (in supplementary papers) on the psychological assessments (Questionnaires for Study Assessments) to better appreciate the relationship in dispositional pain and the potential changes in pain responses due to the respective interventions.

Inclusion of Women and Minorities: Participants will include all sexes and races. We plan to screen from over 2500 cLBP patients from the ACTRI's pain recruitment service, 11 separate providers, and the local community. Based on the latest San Diego-based demographic consensus, we plan to recruit 60% White, 16% Asian, 7% Black, 0.5% Native American, 0.5% Pacific Islander, 12% Other race, 5% two or more races (We expect that 29% of our participants will be Hispanic or Latino). If necessary to obtain minority representation, under-represented racial groups will be targeted specifically for recruitment.

General Considerations:

Data for all individual participants randomized or exposed to study drug will be presented in data listings. Continuous data will be summarized using the following descriptive summary statistics: the number of subjects (n), mean, SD, SE, median, minimum value (min), and maximum value (max). Categorical data will be summarized using counts and percentages.

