Pre Rest + SLR: After identifying the appropriate angle/height to induce a 2-point pain increase, patients will lie in the supine position and will be instructed to “rest with your eyes closed” for 5 minutes. VAS pain ratings will then be collected. With the aid of a technician, patients will then lift their legs to the angle/height calibrated to produce a 2-point VAS pain increase. After 5 minutes, we will collect pain ratings.

Post Rest + SLR: We will wait 10 minutes before continuing the study to control for the time spent administering the drug/saline bolus take effect. VAS pain ratings will be collected after 10 minutes. We will then match the procedures employed in Pre-Rest + SLR.

Post Rest + Heat: A thermal probe will be placed on the back of the “unaffected” calf while patients lie in the supine position. They will be instructed to “rest with your eyes closed” for 8 minutes. We will then match the procedures employed in Pre Rest + Heat.

Patient Randomization:

After successful completion of session 1, participants will be randomized to their respective group. Randomization will be tracked in the Screening/Enrollment Log that is maintained by the clinical

coordinator. Randomization will be stratified so that each sex will have their respective list of randomization codes. Males and females will be randomized without replacement across a block of 60 codes using an Excel-based random number generator. Male and female participants will be randomized within three days of their respective scheduled psychophysical training session. The two treatment arms (mindfulness meditation = A; non-mindfulness meditation =B) will be permuted with respect to treatment assignment, in a double-blind fashion, respectively. We will employ a similar randomization procedure within each group to determine when (i.e., Session 6 or 7) each participant will receive naloxone and saline in a crossover manner.

Sessions 2-5: Regimen:

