Non-mindfulness Meditation Training: The main purpose of the non-mindfulness meditation regimen is to serve as an active control for a crucial, essential element of mindfulness meditation (i.e., mindful attention to breath and non-reactivity to sensory events)(Zeidan, Johnson et al. 2010, Zeidan, Emerson et al. 2015). This regimen is designed so that the primary difference between the mindfulness and non-mindfulness meditation training is the mindfulness meditation group’s explicit mindfulness-based instructions (e.g., mindful attention to the breath). The non-mindfulness meditation group will be told that they are randomly assigned to the meditation group (Zeidan, Johnson et al. 2010, Zeidan, Emerson et al. 2015). In each of the four 20-minute training sessions, participants will be instructed to close their eyes, and to take a deep breath “as we sit here in meditation” every 2-3 minutes (Zeidan, Johnson et al. 2010, Zeidan, Emerson et al. 2015). All other aspects (training room, posture, facilitator, time providing instruction) of the non-mindfulness meditation intervention will be matched.

Sessions 6 & 7: Post-Regimen Session: We will employ a double-blinded crossover design to correspond to the administration of the opioid antagonist, naloxone and placebo-saline across two separate sessions at UCSD’s Altman Clinical and Translational Research Institute (ACTRI). A total of 30 subjects in each group will receive naloxone in Session 6 and saline in Session 7. Conversely, the other 30 subjects in each group will receive saline in Session 6 and naloxone in Session 7. After successful completion of their respective regimen, participants will report to the ACTRI. A research technician will greet patients as they arrive to the ACTRI and guide them to the clinic room. Next, the research technician will issue study assessments to the participant. ACTRI nurses will then administer an opiate-focused urine drug screening to confirm that no participants are using opioids to remove the risk of opioid withdrawal symptoms during naloxone administration, and a pregnancy test (if applicable). Weight will be subsequently measured to confirm the prescribed drug dosage. Next, the

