Patients will return to the ACTRI to complete session 7 and will follow the same procedures (except for drug administration) as Session 6. Participants must wait 2 days to participate but no longer than 7 days to complete Session 7. Drug symptomology will be assessed after each session.

Primary Outcome Measure(s):

1. Visual Analog Scale (VAS) and numerical rating scales (NRS): Pain ratings (VAS pain intensity, VAS unpleasantness, and numerical pain ratings) will be assessed in response to the straight leg raise test.
2. exploratory outcomes include those corresponding to "heat induced pain ratings" (i.e. thermal stimulation), and lying supine. The minimum rating ("0") is designated as "no pain" whereas the maximum ("10") is labeled as "most intense imaginable" or "most unpleasant imaginable." Higher numbers correspond to higher pain.
 - a. We will collect naloxone and saline induced changes in pain intensity and pain unpleasantness ratings

Sample Size Determination: Our targeted sample size is 60 cLBP patients (30/group). To conduct group comparisons among the two primary outcomes (naloxone + saline induced changes in pain intensity + unpleasantness) and to ensure an overall type I error rate < 0.05, we used conservative Bonferroni corrections ($p = .025$) in all power calculations. Employing the pilot data corresponding to our previous work (Wells et al., 2020), we fit repeated measures ANOVA models that include indicator

variables for group (mindfulness vs. sham) and drug (naloxone vs. saline). The estimated square root of mean square errors is 0.23 (23%) and 0.30 (30%) for pain intensity and pain unpleasantness, respectively. Thirty subjects will provide 80% power to detect a pain rating difference of 22% between the naloxone and saline conditions in the non-mindfulness group with an estimated SD of 0.3 (30%). We expect no meaningful differences in pain reductions between naloxone and saline infusion during mindfulness meditation. Thus, we will have 80% power to detect a significant group X drug type interaction. Finally, 30 subjects/group will provide 80% power to detect a significant group difference of 19% for pain intensity and 24% for pain unpleasantness. Such effect sizes parallel those observed in our pilot data (Wells et al., 2020). Statistical power will be also greater when pre-regimen pain ratings are entered as covariates to reduce residual variance.

Questionnaires for Study Assessments:

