Drug Administration: All studies will be conducted with the supervision of ACTRI nurses in the ACTRI. As previously conducted (Zeidan, Adler-Neal et al. 2016), a 0.15mg/kg bolus dose of naloxone (Naloxone HCl, Amphastar Pharmaceuticals) or 25ml of normal saline will be administered over 10 minutes via the IV line of the antecubital vein of the non-dominant arm. Onset of naloxone-induced opioidergic antagonism occurs within 2 min of infusion and exhibits an average half-life of 64 min (Ngai, Berkowitz et al. 1976). To further ensure that naloxone will antagonize opioid receptors for the study entirety, we will administer a supplementary maintenance intravenous infusion dose of 0.15 mg/kg/h naloxone or saline immediately after bolus infusion ceases. The duration of the study from the onset of IV infusion to completion will be no more than 25 (average time of infusion = approx. 15 minutes). Only the study physicians, research pharmacist, and study coordinator will be aware of participant drug assignment.

Sample Size Determination & Power:

Assuming a conservative 20% dropout rate, we will recruit and randomize a total of 74 cLBP patients (n=37/group) to a mindfulness meditation or non-mindfulness meditation regimen. To conduct group comparisons among the two primary outcomes (naloxone + saline induced changes in pain intensity + unpleasantness) and to ensure an overall type I error rate < 0.05, we used conservative Bonferroni corrections (p= .025) in all power calculations. Employing the pilot data corresponding to preliminary findings and our previous work [22], we fit repeated measures ANOVA models that include indicator variables for group (mindfulness vs. non-mindfulness), drug (naloxone vs. saline), and session order. The estimated square root of mean square errors is 0.23 and 0.30 for pain intensity and pain unpleasantness, respectively. Thirty participants per group will provide 80% power to detect a group difference of 0.19 for pain intensity and 0.24 for pain unpleasantness. Such effect sizes are consistent with those observed from our pilot data. Statistical power will be also greater when pre-regimen pain ratings are entered as covariates to reduce residual variance.

Data Analyses and Interpretation:

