10. HUMAN SUBJECTS

Total number of subjects to be enrolled at UCSD

Our targeted sample size is 60 cLBP (30/group). We have exhibited a relatively low attrition rate on previous work, thus we request permission to enroll 74 participants with the goal of retaining 60 participants.

Age: Age will range between 18 and 65 years.

Sex: We will have equal males and females in each group. Groups will be matched by age and sex (15 males/15 females).

Ethnic background: We will include all ethnicities.

Health status: Participants must have a chronic low back pain diagnosis.

All study participants will be recruited from the ACTRI and the local community. We will employ our NIH-approved exclusion and inclusion criteria delineated in previous studies examining cLBP [27; 37; 42] as described below.

Eligibility Criteria: Patients will qualify for the study if medical evaluation demonstrates chronic low back pain that is evoked by lifting the legs. Existing medical records, per physician discretion and low back examinations will confirm diagnosis. Study physicians will confirm diagnosis (Fardon 2001, Wasan, Davar et al. 2005, Jamison, Ross et al. 2010, Wasan, Loggia et al. 2011, Fardon, Williams et al. 2014).

Inclusion criteria include those who:

- a) are between 18-65 years old;
- b) have ongoing chronic pain (pain intensity ≥ 3 on a 0-10 VAS);
- c) have radicular pain for at least 3 months;
- d) are not using other pain management procedures (i.e. CBD oil products) during the study period;
- e) are not taking opioids;
- f) if female and of a child bearing potential age, are not pregnant or nursing mothers;
- g) have not had back surgery within a year of the study start date;
- h) lack sensory/motor deficits that preclude participation in pain-inducing procedures;
- i) have no meditation experience;
- j) are straight leg raise test positive
- k) do not have any known allergies to naloxone or similar drugs

l) do not have a history of syncope and/or fear of needles/blood.

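### The drug-order counts for Sessions 6 and 7 add to 60 per group, twice the planned 30, and no other per-order count is given

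*Protocol*

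**What the plan says.** Protocol section 9, under Sessions 6 & 7, sets the crossover allocation in two consecutive sentences: "A total of 30 subjects in each group will receive naloxone in Session 6 and saline in Session 7", and "Conversely, the other 30 subjects in each group will receive saline in Session 6 and naloxone in Session 7".

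The rest of the plan works to a different size:

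- Protocol section 9, Sample Size Determination: "Our targeted sample size is 60 cLBP patients (30/group". The SAP's sample-size paragraph gives the same target.
- Protocol section 10: "Our targeted sample size is 60 cLBP (30/group", and "Groups will be matched by age and sex (15 males/15 females".
- Protocol section 9, Sample Size Determination & Power: "Assuming a conservative 20% dropout rate", "we will recruit and randomize a total of 74 cLBP patients (n=37/group".

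The Patient Randomization paragraph in section 9 describes separate lists for each sex and a block of 60 codes. For drug order it says only "We will employ a similar randomization procedure within each group to determine when" each participant receives each infusion. It gives no count per order.

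Session order appears in the pilot model described under Sample Size Determination & Power. It is not named in the primary ANOVA of the protocol (Data Analyses and Interpretation) or of the SAP.

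**The concern.** These counts are an allocation instruction, and they cannot be carried out at the planned size. Anyone who builds the order list has to guess the intended numbers, because no other section supplies them.

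Balance of order matters because each participant's naloxone and saline ratings come from different days. If the two orders are unequal within a group, and the response to the manipulation changes between Session 6 and Session 7, part of that change is counted as a drug effect. The trial's main inference is a group-by-drug interaction: a naloxone-saline difference expected under non-mindfulness meditation and none under mindfulness. Unequal order splits that differ between the groups would feed into that interaction, and the planned ANOVAs name no term that would take it out.

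**Working it through.** **1. The planned size, reproduced.** Inputs from Sample Size Determination & Power: alpha 0.025 (two-sided assumed, as sidedness is not stated), power 80%, differences 0.19 and 0.24, root mean square errors 0.23 and 0.30.

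n per group = 2 × [(z₀.₉₈₇₅ + z₀.₈₀) × SD / difference]², with z₀.₉₈₇₅ + z₀.₈₀ = 2.241 + 0.842 = 3.083.

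- Intensity: 2 × (3.083 × 0.23 / 0.19)² = 27.9, so 28.
- Unpleasantness: 2 × (3.083 × 0.30 / 0.24)² = 29.7, so 30.

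The larger value is the stated 30 per group. Dropout: 60 / 0.80 = 75, against the stated 74, which is close enough. So 30 per group is the figure with a derivation behind it.

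**2. The order counts.** 30 + 30 = 60 per group, and 2 × 60 = 120 in total. The plan has 30 per group (60) completing and 37 per group (74) randomised. Dropout does not close the gap, since 37 is still well below 60. The sex split agrees with the smaller figure: 15 + 15 = 30.

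**3. What could follow (assumed list).** Assume one list of 30 naloxone-first and 30 saline-first codes per group, randomly permuted, with only the first 30 used. The number X who get naloxone first is hypergeometric (60 codes, 30 naloxone-first, 30 drawn):

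| Quantity | Result |
|---|---|
| P(X = 15) | 0.203 |
| Same in both groups | 0.203² = 0.041 |
| SD of X | 1.95 |
| Central 95% range | 11 to 19 |
| P(12/18 or worse, either way) | 0.196 |

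If 37 codes are used, the nearest split (18/19) occurs with probability 0.404.

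**4. Effect on the contrast.** Let p be the Session 6-to-7 change in the analysed pain change, n₁ the number naloxone-first and n₂ the number saline-first. The naloxone-first participants contribute (drug effect − p), and the saline-first participants (drug effect + p). The unadjusted mean is therefore the drug effect + p × (n₂ − n₁)/(n₁ + n₂).

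- At 12/18: 6/30 = 0.2 × p.
- Average absolute multiplier over the distribution in step 3: E|30 − 2X|/30 = 0.10.
- Group-by-drug interaction with 12/18 in one group and 18/12 in the other: 0.2 + 0.2 = 0.4 × p. Equal imbalance in both groups cancels if p is the same in both.

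**5. With corrected counts.** Take 18/19 among the 37 randomised, and let 30 complete at random (hypergeometric: 37, 18, 30). An exact 15/15 split occurs in 31% of cases, and 12/18 or worse in about 4%, down from about 20%.

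**The case against.** The strongest reply is that this is a drafting slip. The likely intent is 30 per order across the whole trial, that is 15 per group. Enrolment of 74 is requested, and the monitoring committee reviews at 20, 40, 60 and 74 completers, so no one would recruit 120. That is probably right, but it is an inference: the words that make it 60 per group stand in both sentences, and no other section corrects them.

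Several further points stand and limit the consequence:

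- The randomisation paragraph does not refer to these counts, and nothing shows that a 30 + 30 list was built for each group. Step 3 is a scenario. If the order lists are also split by sex, it does not apply as written.
- A reader might infer that the order would be unbalanced, or that the drug contrast is systematically biased. The documents do not support this. A random half of a 30 + 30 list is balanced in expectation; what is lost is the guarantee.
- A reader might also infer that drug order is the only safeguard against session effects. It is not. The leg raise is recalibrated in each session, ratings are taken before the bolus, and the SAP analyses the change from supine to leg raise. Additive shifts between days are largely removed. What remains is a change in the response itself, such as growing skill in meditating.
- Part of the risk comes from the block of 60 codes in the randomisation paragraph. If each sex has such a list, it too would be only partly used, and correcting the counts alone would leave that in place.

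**Conclusion.** The point holds as a count contradiction. The stated order counts imply 60 per group and 120 in total, against 30 per group (60) planned and 37 per group (74) randomised, and nothing in either document supports the larger figure. This part is certain.

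The consequence is smaller and conditional. It needs the assumed 30 + 30 list, use of only half of it, no order term in the analysis, and a session effect on the pain change that the within-session references leave in place. Under those conditions the typical leakage is about a tenth of that effect, and a fifth at a 12/18 split. Because the documents give no size for the effect, no bias in pain units can be stated. The contradiction also gives no reason to think that the trial needs 120 participants: the power inputs reproduce 30 per group. Severity is minor to moderate.

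**What to change.** 1. **Reconcile the counts.** In Sessions 6 & 7, state 15 participants per order in each group among the 30 completers, and 18 or 19 per order among the 37 randomised. Check this against the Patient Randomization paragraph, both sample-size paragraphs, section 10 and the SAP.
2. **Specify the order list.** Generate it in small permuted blocks within each group, so that stopping part-way leaves the orders nearly equal. Say whether it is also stratified by sex.
3. **Add session order to the primary ANOVAs in the protocol and SAP.** It must act on the within-person contrast: a Session 6 versus 7 term on the pain change or, equivalently, order crossed with drug. A between-person order main effect alone would not adjust the naloxone-saline difference. Take the post-hoc comparisons from the same model, since separate paired t-tests would be unadjusted. This covers imbalance left by dropout, which step 2 cannot prevent.
4. **If the list has already been used,** leave the allocation as it is, report the realised split by order in each group, and rely on the order term.

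The cost is a short protocol correction, a regenerated list if it is still unused, and one added model term in each document. No extra participants are needed.

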research technician will issue study assessments to the subject. We will recalibrate each participant's leg raise height/angle required to elicit a 2-point pain increase employing the methods described in Session 1. An ACTRI nurse will then insert the IV catheter into the non-dominant arm of each participant. As previously employed (Zeidan, Adler-Neal et al. 2016) for safety purposes, blood pressure, respiration, oxygen saturation, and heart rate will be systematically monitored/recorded. These sessions should take approximately 1.0 hour to complete.

Pre Rest + Heat: A thermal probe will be placed on the back of the "unaffected" calf while patients lie in the supine position. They will be instructed to "rest with your eyes closed" (~ 5 minutes). We will administer a "Heat" series that includes 10 alternating, 12-second plateaus of noxious (49°C) and 35°C stimulation. After completion, we will collect pain ratings.

Pre Rest + SLR: The procedures employed in Pre Rest + SLR will be matched to those employed in Session 1. Briefly, patients will lie in the supine position and be instructed to "rest with your eyes closed". VAS pain ratings will then be collected. With the aid of a technician, participants will then lift their legs to the angle/height calibrated to produce a 2-point VAS pain increase. After completion, we will collect pain ratings.

Bolus: An ACTRI nurse will then initiate the naloxone/saline bolus (based on weight) for approximately 8 minutes.

Pre Meditation + SLR: After completion of the bolus (~8 minutes), a study technician will aid participants to lift their legs to the height/angle calibrated to produce a 2-point VAS pain increase. Participants in the mindfulness and non-mindfulness meditation groups will then be instructed to "begin meditating until the end of the session" (Zeidan, Martucci et al. 2011, Zeidan, Emerson et al. 2015). An ACTRI nurse will then initiate the naloxone or placebo-saline infusion. After completion, we will collect pain ratings.

Post Meditation + Heat: A thermal probe will be placed on the back of the "unaffected" calf while patients lie in the supine position and during meditation. We will administer a "Heat" series that includes 10 alternating, 12-second plateaus of noxious (49°C) and 35°C stimulation. After completion, we will collect pain ratings.

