#### Primary outcomes

- Numerical pain ratings while lying in the supine and in response to the straight leg raise test (SLR), respectively.

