#### Exploratory outcome

- SF-12 Health Survey (SF-12): This is a 12-item version of the SF-36 item Health Survey designed to assess general mental and physical functioning, and overall health-related quality of life.

**Statistical Analysis Plan:** To test the primary hypotheses, a 2 (group) X 2 (rest vs. manipulation) X 3 (baseline vs. naloxone vs. saline) mixed model ANOVA will be employed to test differences in the change in pain from supine to straight leg raise test (SLR 1; SLR 2) within and across each testing session. Significant interactions will be explored using post-hoc paired simple effects tests to test the hypotheses that non-mindfulness meditation but not mindfulness induced analgesia will be reversed by administration of naloxone but not saline. Between group comparisons will also be explored with simple effects tests.

Secondary and exploratory outcomes will be assessed with a 2 (group) X 2 (baseline vs. post-intervention) by testing between and within group differences comparing baseline vs. post-study assessments. Simple effects tests will interpret significant main effects and interactions.

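### Sessions 6 and 7 describe no supine rating between the bolus and the second leg raise; adding one, and naming the SLR 2 reference in the SAP, is a cheap improvement

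*Protocol*

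**What the plan says.** **Session 1 (Protocol section 9).** Pre Rest + SLR has a 5-minute supine rest, a rating, the raise, and a rating 5 minutes later. Post Rest + SLR then imitates the bolus period: "We will wait 10 minutes before continuing the study to control for the time spent administering the drug/saline bolus take effect". It continues: "VAS pain ratings will be collected after 10 minutes. We will then match the procedures employed in Pre-Rest + SLR". SLR 2 therefore has its own supine rating, taken after SLR 1.

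**Sessions 6 and 7 (same section).** Pre Rest + SLR is said to match Session 1. It is followed by a bolus of about 8 minutes, and then: "After completion of the bolus (~8 minutes), a study technician will aid participants to lift their legs". Participants are next told to "begin meditating until the end of the session", the maintenance infusion starts, and pain is rated once the step is complete. The heat series follows, also during meditation. No rating is described between the SLR 1 rating and the second lift. Drug Administration gives a different bolus length: it "will be administered over 10 minutes via the IV line of the antecubital vein of the non-dominant arm".

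**Outcomes and analysis.** The protocol puts ratings obtained with heat ("i.e. thermal stimulation), and lying supine") among the exploratory outcomes. The SAP's primary outcome is "Numerical pain ratings while lying in the supine and in response to the straight leg raise test (SLR), respectively". Its model has baseline, naloxone and saline as session levels and is used to "test differences in the change in pain from supine to straight leg raise test (SLR 1; SLR 2) within and across each testing session". It does not name the supine rating that serves as the reference for SLR 2.

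**The concern.** The SAP's dependent variable is a difference, so its meaning depends on what is subtracted. Followed as written, the drug sessions offer only a supine rating that predates both SLR 1 and the drug, while Session 1 offers a fresh one. Any shift in resting pain between that rating and SLR 2 would then stay in the SLR 2 change on drug days but could be subtracted out at baseline. This affects the within-group contrasts with baseline, which show whether there is meditation analgesia to reverse.

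The second consequence concerns mechanism. Every rating described after the bolus is taken during meditation. If naloxone alters resting pain in these patients, who must enter with ongoing pain of at least 3 out of 10, that effect appears in the within-group naloxone-versus-saline simple effects and cannot be told apart from reversal of meditation analgesia.

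**Working it through.** The plan states no figure for this point, so the check traces the schedule, works through the change score, and tests timing and cost.

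**1. Schedule, in minutes from the SLR 1 lift.** Inputs: rest 5, SLR rating at 5 and wait 10 (Session 1); bolus about 8 (Sessions 6 and 7) or 10 (Drug Administration). Sessions 6 and 7 give no rating delay, so Session 1's 5 minutes is assumed.

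| | Session 1 | Sessions 6 and 7 |
|---|---|---|
| Supine rating before SLR 1 | yes | yes |
| SLR 1 rating | 5 | 5 |
| Wait or bolus ends | 5 + 10 = 15 | 5 + 8 = 13, or 5 + 10 = 15 |
| Supine rating after it | yes | none described |
| SLR 2 lift | 15 + 5 = 20, or 15 if the wait replaces the rest | 13 or 15 |
| Age of latest supine rating at SLR 2 lift | 0 | 13 or 15 |

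If SLR 1 were rated at once, the last figure would be 8 or 10.

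**2. Change score.** Let S be resting pain at the first supine rating, e the evoked rise, r any shift in resting pain from time or SLR 1, d the drug effect on resting pain, m the relief from meditation, and v the part of m that naloxone reverses. Effects are taken as additive.

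With the supine ratings described, using the latest one available:

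- Session 1: (S + r + e) − (S + r) = e
- Saline: (S + r + e − m) − S = e + r − m
- Naloxone: (S + r + d + e − m + v) − S = e + r + d − m + v

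Saline minus baseline is r − m instead of −m. Naloxone minus saline is d + v instead of v; r drops out if it is equal on the two days. Group x drug, with groups A and B, is (d_A + v_A) − (d_B + v_B), which equals v_A − v_B when d_A = d_B.

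With a supine rating at bolus end as reference, the three changes are e, e − m and e − m + v, and naloxone minus saline is v.

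The documents give neither r nor d. If each is assumed to lie between 0 and 1 point, the offset against baseline is 0 to 1 point on saline (r) and 0 to 2 points on naloxone (r + d), beside a targeted evoked rise of 2 points.

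**3. Leftover SLR 1 pain.** The protocol says a raise increases pain for 10 to 15 minutes. With both raises rated at 5 minutes, the SLR 2 rating falls at 13 + 5 = 18 or 15 + 5 = 20 minutes, past that window, so the leftover is 0. Under an assumed linear decay, 2 × (1 − t/T) with T at most 15:

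- only one raise rated at once, 8-minute bolus: t = 13, 2 × (1 − 13/15) = 0.27 points
- only one rated at once, 10-minute bolus: t = 15, 0 points
- both rated at once, 8-minute bolus: t = 8, 2 × (1 − 8/15) = 0.93 points

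The non-zero cases depart from Session 1's 5 minutes.

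**4. Infusion time.** The heat series is 10 × 12 s = 2 minutes, or 4 if ten pairs are meant. With a 10-minute bolus and a 5-minute SLR step, the total is 10 + 5 + 2 to 4 = 17 to 19 minutes. If the post heat step keeps Session 1's 8-minute rest, it is 10 + 5 + 8 + 2 to 4 = 25 to 27. That second reading fits Drug Administration: 5 + 8 + 2 = 15, its approximate average infusion time, and 15 + 10 = 25, its maximum (printed without a unit, taken as minutes). A further 5-minute rest would give 30 to 32.

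**The case against.** The strongest reply is that this argues from silence. The SAP names no SLR 2 reference in any session, so the sponsor could use the first supine rating throughout, which removes the asymmetry. The Sessions 6 and 7 text is openly abbreviated. The supine steps mention only VAS ratings although the SAP's primary outcome is numerical, so they are evidently not a full list, and a rating after the bolus may have been intended. The baseline comparison is imperfect anyway: Session 1 is on another day, before training and without infusion, and the leg angle is recalibrated later. A pre-drug reference is also a legitimate choice, since it keeps a resting drug effect in the estimate.

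Most of this stands, and it rules out three stronger readings that a reader might infer:

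- *The SAP definitely subtracts an outdated reference.* It does not say so; it leaves the pairing open.
- *The naloxone-versus-saline or group x drug test is biased by the schedule.* Reference and timing are the same on both drug days, and a resting drug effect common to both groups cancels from the interaction.
- *Leftover SLR 1 pain contaminates SLR 2.* On the 5-minute rating time it is about 0.

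The reply does not remove the gap. The wording that matches Session 1 covers only the first raise. Using the first supine rating everywhere still leaves r and d in the score. A rating at bolus end forecloses no analysis, because the change can still be computed from the pre-drug rating.

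**Conclusion.** The point holds as a cheap improvement. As described, the drug sessions lack the supine rating that Session 1 takes at the corresponding moment, and the SAP does not fix the SLR 2 reference. Within-group baseline-versus-drug contrasts on the SLR 2 change may not be like for like, by r on saline and r + d on naloxone. The within-group naloxone-versus-saline simple effects contain d + v.

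The size is unknown because the documents give no value for r or d; the SLR 1 part of r is about 0 on the stated timing. The conclusion assumes that the text is followed as written, that effects add, and that carry-over is equal on the two drug days. The added rating would isolate only a resting drug effect. A naloxone effect on the evoked rise itself would still be mixed with reversal.

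**What to change.** 1. In Sessions 6 and 7, take one supine rating, numerical and VAS, at the end of the bolus, before the SLR 2 lift and the meditation instruction.
2. In the SAP, name the supine rating paired with SLR 1 and with SLR 2 in each session, by the same rule in all three. Report the SLR 2 change against both the pre-drug and the post-bolus supine rating.
3. Give one bolus duration in the Sessions 6 and 7 steps and in Drug Administration.

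Do not add a 5-minute rest after the bolus. If the post heat step keeps 8 minutes, the total with a 10-minute bolus is already 25 to 27 minutes against a limit of 25.

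The cost is one extra rating per drug session, under a minute; items 2 and 3 are wording. If data have already been collected without this rating, use the first supine rating as the reference in all three sessions. State as a limitation that shifts in resting pain, including any drug effect, remain in the SLR 2 change.
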